An adverse event (AE) is any untoward medical occurrence in a subject temporally associated with participation in the clinical study or with use of the experimental agent being studied. An adverse finding can include a sign, symptom, abnormal assessment (laboratory test value, vital signs, electrocardiogram finding, etc.) or any combination of these. An adverse event can be an expected side effect that is of a serious nature, or an unexpected side effect/event regardless of severity. All adverse events will be graded as to their attribution (related or unrelated) and their severity.

A Serious Adverse Event (SAE) is any adverse event that meets one of these criteria:

- The event results in death
- The event is life-threatening
- The event results in an inpatient hospitalization or prolongation of existing hospitalization
- The event results in permanent or severe disability or permanent damage
- A pregnancy results in a congenital anomaly or birth defect
- Based on appropriate medical judgment, the event may jeopardize the subject's health and may require medical or surgical intervention to prevent one of the other outcomes listed above

Adverse event documentation

1. Every event that is reported to the principal investigator or research staff by the subject or medical staff caring for the subject which meets the criteria for adverse event will be documented in the Case Report Form (CRF). Additionally, the event will be documented in the **adverse events log** located on the study folder within an encrypted drive.
2. Adverse event documentation will include description of the event, when and how it was reported, as well as any official chart records or documentation to corroborate the event; determination of attribution)
3. Adverse events will be reported to the CPHS as per CPHS policy.

Stopping Rules

In case a patient enrolled in the study presents an emergency condition, the following steps are to be followed in addition to regular clinical procedure:

1. The Principal Investigator will be contacted in order to report the serious incident. His office number and cellphone are located on a binder in unit 2D.
2. [name] will then determine whether the incident is related to the Ketamine/Placebo administration and give further instruction.
 - a. Should staff be instructed to break the blind, they can look up a specific patient in the **2D ketamine trial enrollment list**. This list is the first page of the binder located in unit 2D. The binder also contains possible side effects and the contact information of the PI, the medical monitor and the study team.
 - b. In the Nurse Supervisor's Office there is an Orange container. The staff will ask the nurse supervisor to break the seal on the container and locate the list on the bottom slot. (This is only to be used for emergencies with [name] approval.) After locating the file, staff will match the patient's medication number to determine the medication given.
3. The medical monitor will be informed of the event within 48 hours.

IRB NUMBER: HSC-MS-17-0903
IRB APPROVAL DATE: 10/09/2019

Safety Review Plan and Monitoring

Oversight of participant safety includes review of adverse events as well as study progress, data integrity and study outcomes.

1. The principal investigator will review all adverse events immediately if he is at the facility. If the event occurs while the PI is not at the facility, the staff will contact the PI via cellphone. In turn, the PI will make determinations on whether the adverse event is serious, related and or expected.
2. All serious adverse events such as changes in systolic or diastolic blood pressure (BP) $>180/100$ mmHg or heart rate >110 beats/minute, will be reported to the independent medical monitor within 48 hours.
3. The Principal Investigator is responsible for reviewing study progress (e.g., recruitment, retention, protocol adherence) on a quarterly basis.
4. The Principal Investigator will submit an annual report to the independent medical monitor including a summary of the items covered in the biannual meetings-- List and summary of adverse events, whether adverse event rates are consistent with pre-study assumptions, summary of recruitment and retention and reason for dropouts and whether the study is on track to be completed and accomplish the stated aims.
5. The annual report will be reviewed and signed by the medical monitor and submitted annually to CPHS.

Alternative therapies for depression: Currently available antidepressants, i.e. tricyclic antidepressants (TCAs), monoamine oxidase inhibitors (MAOIs), selective serotonin reuptake inhibitors (SSRIs), serotonin norepinephrine reuptake inhibitors (SNRIs) and atypical antidepressants (bupropion, mirtazapine, vilazodone, etc.), and neuromodulatory therapies, i.e. electroconvulsive therapy (ECT), transcranial magnetic stimulation (TMS), vagal nerve stimulation (VNS) and deep brain stimulation (DBS), are effective treatments for Depression. Several psychotherapeutic modalities, i.e. cognitive-behavioral therapy (CBT) and interpersonal therapy (IPT), are also effective and are frequently used in combination with medications. While individuals with depression often report suicidal thoughts, none of these treatments have a demonstrated rapid effect of suicidal ideation.

Participants will be informed and/or reminded that these alternative treatments for suicide or depression are available to them in the community before enrollment into this protocol. They will be informed that standard of care on psychiatric inpatient units may include pharmacologic and psychotherapeutic approaches which will be started right away. They will also be reminded that they can be transferred to a different psychiatric facility for follow-up care. This approach will ensure that patients are clearly informed of the standard of care that is available to them before being exposed to experimental risks.

Early holding rule includes an overall improvement lower than 20% (based on SSI scores) in first 15 patients randomized and the present of any serious and unexpected adverse effect.

Data handling and record keeping

As is standard of care on our unit, we will require participant authorization to release any medical information. Hard copy research data/records will be de-identified (so no individual will be identified by name) and stored double-locked (in locked cabinets in a room that is locked when unoccupied).

Electronic data with identifiers (including biomarkers) will be saved on password-protected computers on secured servers (encrypted drives). Biomarkers data will be maintained on a secure internet-based

IRB NUMBER: HSC-MS-17-0903
IRB APPROVAL DATE: 10/09/2019

server. Only study investigators will have access to the data. De-identified results from clinical trials will be posted on ClinicalTrials.gov.

For Stored Samples: Biological samples will be kept in dedicated freezers without patient identifiers. Results will be published as group data without the use of specific identify identifiers. Sample(s) and date(s) will be stored using assigned code(s) and kept in locked storage. Electronic health information and research data will be kept on password-protected computers with encrypted drives. Only study investigators will have access to the stored samples.

Special Precautions: Samples and data will be stored using codes that we assign. Data will be kept in password-protected computers. Samples will be kept in locked storage. Only study investigators will have access to the samples and data.

Statistics

Our outcome analyses will focus on examining the acute effects and duration of intranasal ketamine treatment during inpatient psychiatric hospitalization. As a primary outcome, we will examine the efficacy of intranasal ketamine for preventing suicidal behavior and ideation among adult patients in a current depressive episode at day 1. Our primary outcome analysis seeks to answer two questions: 1) will intranasal ketamine work acutely compared to placebo, and 2) how long will this effect persist? Effect sizes will be calculated for intranasal ketamine treatment. In the primary outcome analysis, two dichotomous primary outcome measures will be examined in the evaluation: 1) the presence or absence of suicidal ideation, and 2) the presence or absence of suicidal behavior as measured using the C-SSRS and SSI. Our secondary outcome analysis will include an examination of 1) the effects of intranasal ketamine for suicidal ideation while controlling for improvements in depression and other dimensions 2) the potential role of recent alcohol abuse and previous alcohol dependence in the rapid anti-suicidal effects of intranasal ketamine. The symptom severity ratings of SSI, the C-SSRS total score and, as well as changes in MADRS scores will be utilized as primary and secondary outcomes, respectively. Normality assumptions for continuous variables will be examined. Baseline characteristics will be compared between responders and non-responders with the Mann-Whitney U test for continuous variables and the chi-square test for categorical variables. Changes between two time-points for continuous variables were tested with paired t tests, and associations between continuous variables will be quantified with the Spearman correlation coefficient. Random effects models will be performed to quantify changes in clinical score and its component items over time and to compare temporal differences between eventual responders and non-responders.

Analyses of cross-sectional data with missing values will utilize multiple imputation (Proc MI and Proc MIANALYZE, SAS v. 9.3), while longitudinal analyses will rely on maximum likelihood (in the Bayesian context). Multiple imputation, maximum likelihood, and explicitly modeling missing data in the Bayesian approach are all robust to data missing at random. Sensitivity analyses will permit evaluation of the robustness of findings to missing data assumptions. Pattern-mixture modeling methods will address any identified non-ignorable missing data patterns.

Preliminary data analyses will inspect baseline group differences as well as correlations between baseline covariates and specified criterion variables. Baseline covariates demonstrating a correlation

IRB NUMBER: HSC-MS-17-0903

IRB APPROVAL DATE: 10/09/2019

with both predictors and outcome variables, meet criteria for being potential confounders, and will result in two sets of analyses: one in which the relevant variable is included as a covariate and one in which it is not. This will determine the degree to which any group differences might confound conclusions regarding treatment. Analyses will proceed in parallel using conventional, Frequentist and Bayesian approaches. Frequentist results yield the probability of the observed data, or data more extreme, given that the null hypothesis holds. Bayesian results yield the probability that an alternative holds. Eleven patients per group are required using confidence level of 95% (with $P<0.05$, two-tailed) and power 0.8, based on previous studies using ketamine for depression in placebo-controlled studies reporting response rates of 60% with ketamine and 10% with placebo. The study was designed to detect a moderate to large difference ($d=0.7$) between ketamine vs placebo, based on previous studies using IV ketamine (Wilkinson et al 2018). Treatment effects may be also quantified as mean differences between groups and associated effect sizes are based on standardized mean difference (Cohen's d). All statistical tests were two-sided with an alpha set at 0.05. All analyses were performed using SPSS v. 20 (SPSS Inc., USA) and SAS (version 9.2; SAS, Cary, North Carolina).

References

Andrade C. Intranasal drug delivery in neuropsychiatry: focus on intranasal ketamine for refractory depression. *J Clin Psychiatry*. 2015 May;76(5):e628-31.

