Description of Study Populations: A total of 60 individuals (males and females) between the ages of 21-60 will be enrolled in the study. Two participant populations will be recruited into this protocol. Participant populations are individuals with the following conditions: 1.) current suicidal ideation and past suicide attempt under intranasal ketamine (Group 1, n= 30) and current suicidal ideation and past/recent suicide attempt under placebo (Group 2, n= 15). Group 1 will include two subgroups, with (n=15) or without (n=15) recent abuse of alcohol plus positive personal/family history for alcoholism. The study will take place at a Research Unit at the Harris County Psychiatric Center, UT Houston. Participants at acute risk will be admitted to the HCPC 2D Unit, a secure, but voluntary psychiatric unit, in which there will be nursing staff and physicians available at all hours to respond to any crisis as needed. Subjects will complete an informed consent process and will be systematically screened for inclusion and exclusion criteria. Only participants with a lifetime history of suicide attempt will be enrolled.

Design

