This study will be a double-blind, randomized, placebo controlled trial, evaluating drug-free inpatients (at least 24hs period pre-admission) with depressive episode associated with past suicidal attempt and current active suicidal ideation. Patients will be randomly assigned to intranasal ketamine hydrochloride (50 mg) or saline solution (1 to 1 in both groups, suicide or suicide plus alcohol, with a total of 4 groups). After the single intranasal administration, assessments will occur at +40 min, +240 min, +24 h (phase 1), and +48 h (phase 2). For phase 2, patient may receive their regularly scheduled daily medications if improvement less than 50%. Pts will be subsequently followed up on the suicidal ideation scores until discharge once a day with treatment as usual. This study is expected to take one year to be concluded. Medication should be applied in the first 24hs after admission. There is no approved treatment for suicidal ideation and just a few trials used ketamine for suicidal ideation, none of them evaluating the intranasal route. Thus, a placebo-controlled study is warranted to prevent potential methodological issues. The use of ketamine plus standard care would bias the evaluation of the specific antisuicidal efficacy of intranasal ketamine since standard treatments in some cases may also target suicidality and mood in the short-term.

Assessment of antisuicidal efficacy will be obtained using the Columbia-Suicide Severity Rating Scale (CSSRS) as a screening tool for inclusion (based on "yes" or "no" questions) at HCPC. MADRS item 10 score of 5 or 6 suggests active suicidal risk and will be also used as the threshold for patient inclusion in the ketamine intervention. For those enrolled, the primary efficacy outcome measure will be changes in suicide severity at 24hr post-treatment based on the Scale for Suicide Ideation (SSI) scores, which assesses presence of suicidal ideation and history of suicidal behavior. Secondary outcomes to be administered at each visit include the Montgomery-Åsberg Depression Rating Scale (MADRS), the Young Mania Rating Scale (YMRS), the Clinician-Administered Dissociative States Scale (CADSS), Snaith-Hamilton Pleasure Scale (SHAPS) Alcohol Urge Questionnaire (AUQ) and the Clinician-Administered National Institutes of Health-Brief Fatigue Inventory (NIH-BFI). Inter-rater reliability will be assessed for all ratings, with accepted kappa over 0.8.

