- 5) *Clinician-Administered Dissociative States Scale* (CADSS) is a clinician-administered measure of perceptual, behavioral and attentional changes occurring during dissociative experiences that has been tested in healthy subjects and post-traumatic stress disorder (PTSD). This scale involves 19 self-reported questions and eight observer ratings scored from 0 (not at all) to 4 (extremely). To characterize dissociative responses to ketamine, the CADSS will be sorted into five subscores with apparent face validity based on published scales that also assess dissociative states: body perception, environmental perception, feelings of unreality, memory impairment and time perception (Bremner et al 1998).
- 6) The *Snaith-Hamilton Pleasure Scale* (SHAPS) is an assessment of anhedonia, which has been extensively used by our group. The 14-item measure takes 5 minutes to complete (Snaith et al 1995).
- 7) The *Clinician-Administered National Institutes of Health-Brief Fatigue Inventory* (NIH-BFI) is an assessment of fatigue in the context of depression (Saligan et al 2015).
- 8) *Self-Report: Alcohol Urge Questionnaire* (AUQ) is a multi-item measure of self- reported urges to drink alcohol, predictor of drinking abuse and relapse (Bohn MJ, Krahn DD, Staehler BA 1995) and AUDIT/CIWA.

Although the primary aim of this study to investigate the efficacy of ketamine as a treatment for suicidal thoughts, this investigation is also designed to provide initial data for potential biomarkers of antisuicidal response and the neurobiology of the response process. Sixty six percent of all patients will

IRB NUMBER: HSC-MS-17-0903
IRB APPROVAL DATE: 10/09/2019

receive intranasal ketamine, while only 33.3% will be receiving placebo. We decided not to use active placebo (midazolam) due to the risk of increasing craving for alcohol. After the end of the trial (48hs), all patients will receive treatment as usual as well as lithium, which is a medication that has shown significant antisuicidal properties (Lewitzka et al 2015). All patients will be discharge when presenting no acute suicidal ideation based on C-SSRS and SSI.

Study Population

All study investigators and raters will be blind to assignment. Subjects will complete an informed consent process and will be systematically screened for inclusion and exclusion criteria, as follows:

Inclusion Criteria:

1. Male or female between the age of 21 and 60 years old, voluntary admission.

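### The protocol describes two incompatible designs: the stated total is 60 but the listed groups sum to 45, and allocation is 1:1 in four groups in one place and 2:1 in another

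*Combined protocol and SAP*

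**What the plan says.** Three places in the current text of the combined protocol and SAP fix the size and structure of the trial.

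- **Description of Study Populations.** The total is given as "A total of 60 individuals (males and females) between the ages of 21-60 will be enrolled in the study". The section then says "Two participant populations will be recruited into this protocol" and lists them: "past suicide attempt under intranasal ketamine (Group 1, n= 30") and "past/recent suicide attempt under placebo (Group 2, n= 15"). The ketamine group is subdivided: "Group 1 will include two subgroups, with (n=15) or without (n=15) recent abuse of alcohol". No such division is given for placebo.
- **Design.** Patients are randomised to ketamine or saline "1 to 1 in both groups, suicide or suicide plus alcohol, with a total of 4 groups". No group sizes are given.
- **Text after the list of Clinician Administered Measures.** "Sixty six percent of all patients will" "receive intranasal ketamine, while only 33.3% will be receiving placebo" (one sentence, split by a page break).

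The Statistics section gives two bases for sample size. One is 11 per group for response rates of 60% v 10% (two-sided 0.05, power 0.8). The other is a target standardised difference of d=0.7, for which no power is stated.

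**The concern.** Total sample size, allocation ratio and number of groups are the core of a randomised design, and a reader cannot recover any of the three from this text. No single correction removes the conflict:

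- Changing 60 to 45 leaves the 1:1 ratio and the four groups wrong.
- Raising placebo to 30 leaves the 66%/33.3% sentence wrong.
- Applying 2:1 to 60 gives group sizes that appear nowhere.

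At stake are how many suicidal inpatients are assigned placebo, what power the main comparison has, and whether anyone can verify that the allocation in use is the one approved.

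**Working it through.** **1. The stated total.** Inputs are from Description of Study Populations.
- 15 + 15 = 30 ketamine; 30 + 15 placebo = 45. The stated 60 is not reproduced; the gap is 15 patients, or 15/60 = 25%.

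**2. The ratio.**
- Listed groups: 30/45 = 66.7% and 15/45 = 33.3%. This matches the 66%/33.3% sentence.
- 1:1 within each alcohol stratum gives 50%/50% overall, whatever the stratum sizes. This cannot match that sentence.
- 2:1 on 60: 60 × 2/3 = 40 and 60 × 1/3 = 20. Neither is a listed group size.

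**3. Which statements fit together.**

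| Design | Total | Ketamine v placebo | Fits | Conflicts with |
|---|---|---|---|---|
| 4 × 15, 1:1 | 60 | 30 v 30 | total of 60; Design section; ketamine 30 | placebo 15; 66%/33.3% |
| 3 × 15, 2:1 | 45 | 30 v 15 | all listed group sizes; 66%/33.3% | total of 60; Design section |
| 2:1 on 60 | 60 | 40 v 20 | total of 60; 66%/33.3% | listed group sizes; Design section |

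**4. Does the figure of 11 per group decide it?** The unpooled two-sided formula reproduces it:
- n = (1.960 + 0.8416)² × (0.6×0.4 + 0.1×0.9) / (0.6 − 0.1)² = 7.849 × 0.33 / 0.25 = 10.36, rounded up to 11.
- Two, three or four groups of 11 make 22, 33 or 44. None of these identifies the intended design.

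**5. Power at d=0.7.** The plan names no test for the between-arm contrast on the Scale for Suicide Ideation (SSI), so an unadjusted two-sided t-test at 0.05 is assumed. The noncentrality is 0.7/√(1/n₁ + 1/n₂), with n₁ + n₂ − 2 degrees of freedom.
- 30 v 30: 0.7/0.2582 = 2.711, 58 df, power 76.0%.
- 30 v 15: 0.7/0.3162 = 2.214, 43 df, power 58.1%.
- 40 v 20: 0.7/0.2739 = 2.556, 58 df, power 71.0%.
- Smallest d with 80% power, in the same order: 0.74, 0.91, 0.78.

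**6. Power at 60% v 10%.** Fisher's exact test, two-sided 0.05, summed over all binomial outcomes.
- 30 v 30: 98.5%. 30 v 15: 91.4%. 40 v 20: 97.8%.

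**The case against.** Several points limit what can be claimed.

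- **Enrolled may mean consented.** Consent precedes systematic screening, and the Study Population section foresees people who reach the unit and prove ineligible. So 60 might count people consented and 45 people treated. No passage says so, and this would not reconcile 1:1 with 2:1. It does make the total somewhat less certain as a contradiction than the ratio.
- **Placebo and alcohol status.** A reader might infer that the plan contradicts itself on who is in the placebo group, or leaves patients with alcohol abuse without a control. The documents do not support this. Description of Study Populations is silent on the alcohol status of its 15 placebo patients, which is an omission, and the Design section puts saline in both strata. The pooled primary objective has a placebo control in every version.
- **The allocation list.** A reader might infer that no list could be built. Stopping Rules describes an enrolment list and a sealed list that links medication numbers to treatment. What stands is that these cannot be checked against the protocol.
- **A third placebo number.** Only 15 is written. 30 is derived from 1:1 on 60, and 20 comes from joining two sentences in different sections.
- **Power.** On the only basis for which the plan states 80% power, both designs are adequate. The d=0.7 figures depend on an assumed test. If the analysis adjusted for a baseline covariate correlated 0.5 with the outcome (an assumption), the effective d is 0.7/√0.75 = 0.81, and power is about 87% (30 v 30), 70% (30 v 15) or 83% (40 v 20). The contradiction causes the spread between designs; the unadjusted shortfall below 80% is present in all of them.

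None of this removes the core conflict.

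**Conclusion.** The contradiction is real, lies in current operative text and must be fixed. Total N is 60 or 45, allocation is 1:1 or 2:1, and the structure is four groups or three. The number assigned placebo is 15 as listed or 30 as implied. Two coherent designs appear to be mixed, and the documents do not say which was intended.

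At d=0.7 the choice moves power from 76% to 58%, a difference of 18 percentage points, under an unadjusted two-sided t-test; neither reaches 80% on that assumption. At 60% v 10% both designs are adequately powered. A reader might conclude that the trial is underpowered on every basis because of this inconsistency; the second result shows that it is not.

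The finding that the sections conflict rests on arithmetic alone. Only the power figures depend on assumptions.

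**What to change.** State one design and align Description of Study Populations, Design, and the paragraph after the list of measures.

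- **If 1:1 in four groups:** set Group 2 to n=30 (15 with and 15 without alcohol abuse) and delete the 66%/33.3% sentence.
- **If 30 + 15 at 2:1:** change 60 to 45, correct the 1:1 ratio and the four groups, and state how the 15 placebo patients divide by alcohol status.
- **If 2:1 on 60 was meant**, which no section lists: restate the groups as 40 and 20, give the alcohol split of each, and correct the 1:1 ratio and the listed sizes.

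In Statistics, restate power for the chosen design at d=0.7 and at 60% v 10%, name the test assumed, and say which comparison the 11 per group refers to.

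Investigators and raters are blind and the treatment key is sealed for emergencies. Any check against the list in use should therefore be made by an unblinded person outside the study team, who reports only whether the list matches the text.

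As a separate matter, inclusion criterion 4 requires current alcohol abuse. Read literally, it excludes the patients without alcohol abuse provided for in General Information, Objectives, Description of Study Populations and Design. These passages must be reconciled; the criterion is not evidence for either design.

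**Cost:** a text amendment and one list check. The options differ in substance: 1:1 on 60 means 30 patients on placebo instead of the 15 listed, 30 + 15 has the least power, and 40 + 20 puts 20 on placebo.

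### Every test is set at two-sided 0.05, with no testing order, key secondary outcome or time, or exploratory label for the six secondary scales and the SSI times other than 24 h

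*Combined protocol and SAP*

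**What the plan says.** The Design section fixes one primary measure at one time: "the primary efficacy outcome measure will be changes in suicide severity at 24hr post-treatment based on the Scale for Suicide Ideation (SSI) scores". It then gives the secondary set: "Secondary outcomes to be administered at each visit include the Montgomery-Åsberg Depression Rating Scale (MADRS), the Young Mania Rating Scale (YMRS"), followed by CADSS, SHAPS, AUQ and NIH-BFI, which makes six scales. The schedule is "assessments will occur at +40 min, +240 min, +24 h (phase 1), and +48 h (phase 2"), so there are four post-dose times. SSI scores are also followed daily until discharge.

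The Statistics section says that the primary outcome analysis asks two questions: "will intranasal ketamine work acutely compared to placebo, and 2) how long will this effect persist". The second question brings in SSI at times other than 24 h, and no time is named for it. The same section adds: "Random effects models will be performed to quantify changes in clinical score and its component items over time", with a further purpose, to "compare temporal differences between eventual responders and non-responders". It also plans paired t tests between time points, without saying which pairs. Of the six scales, it names only MADRS as an outcome.

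The error rate is set by one sentence at the end of that section: "All statistical tests were two-sided with an alpha set at 0.05". The list of clinician-administered measures adds five CADSS subscores. The closest thing to an exploratory label, under the same heading, refers to initial biomarker data and not to the clinical scales.

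**The concern.** The words primary and secondary are the only ranking in the plan. Nothing says that a claim of lasting effect requires a positive 24 h result, although the primary hypothesis includes a sustained decrease. Nothing says which time counts for MADRS, anhedonia, craving or fatigue.

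Suppose the 24 h SSI comparison is null. Under the stated rule, an SSI difference at 40 min, 240 min or 48 h, or a difference on one secondary scale at one time, could still be reported as significant at the same nominal level. Because neither the analysis nor the time is fixed for each scale, the choice could be made after the data are seen. In a trial of 60 patients (the listed groups sum to 45), a reader could not tell such an isolated result from chance.

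**Working it through.** The documents state no family-wise error rate for these outcomes, so there is no figure of the plan's own to reproduce.

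**Inputs from the documents.** Alpha is 0.05 two-sided for each test (Statistics). There are six secondary scales, four post-dose times and one primary time, 24 h (Design). CADSS and the mood item of YMRS also serve safety (Design).

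**Assumptions.** There is no true effect on any outcome. The k tests are z tests with a common correlation ρ. The documents give no correlations, so ρ is taken as 0, 0.5 and 0.8.

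**Formulas.** With independent tests, the chance of at least one false positive is 1 − 0.95^k. With common correlation ρ, each test statistic is √ρ·C + √(1−ρ)·E, where C is a shared standard normal variable and E a separate one for each test. The chance is then 1 − E_C{[P(|Z| < 1.96 given C)]^k}, obtained by simulation and checked by numerical integration. The expected number of false positives is 0.05·k, whatever the correlation.

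**Independent case, numbers put in.**
- k = 4: 1 − 0.95^4 = 0.185
- k = 6: 1 − 0.95^6 = 0.265
- k = 16: 1 − 0.95^16 = 0.560
- k = 24: 1 − 0.95^24 = 0.708

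**Results.**

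| Reading of the plan | k | ρ = 0 | ρ = 0.5 | ρ = 0.8 | Expected false positives |
|---|---|---|---|---|---|
| SSI at four post-dose times, 24 h primary included | 4 | 19% | 16% | 11% | 0.2 |
| One test per secondary scale | 6 | 26% | 21% | 14% | 0.3 |
| Four scales without a safety role, at four times | 16 | 56% | 37% | 21% | 0.8 |
| Six scales at four times (widest) | 24 | 71% | 46% | 24% | 1.2 |

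The first row includes the primary test. The three other SSI times alone give at most 1 − 0.95^3 = 14%.

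**Not counted.** The component-item models are left out because the group contrast named with them is responder against non-responder, which does not estimate a treatment effect. The daily SSI scores after 48 h, the CADSS subscores and the paired t tests are left out because the plan does not say how many tests they would give.

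**The case against.** The strongest reply is that the plan does not commit to most of these tests. Giving a scale at each visit is a collection schedule, and the Statistics section specifies no ketamine-against-placebo test of each scale at each time. A reader might infer from the schedule and the alpha sentence that 24 between-arm tests are planned and that at least one false effect is likely. The documents do not support that. The 24-test count is the widest reading of an unspecified plan, and even there the chance passes one half only at low correlation: it is 46% at ρ = 0.5. Scales repeated in the same patients within 48 hours are unlikely to be independent.

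A reader might also infer that "quantify changes in clinical score and its component items over time" multiplies the treatment tests by the number of items on each scale. That does not follow either, because of the responder contrast in the same sentence.

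Other parts of the reply also hold. CADSS and the YMRS mood item serve safety, where a false positive would be a false signal of harm. The plan does separate primary from secondary outcomes, and it plans effect sizes, mean differences and parallel Bayesian analyses, so reporting would not rest on significance alone. The firmly worded secondary hypotheses concern independence from the antidepressant effect, alcohol, biomarkers and safety; none predicts a gain in anhedonia or fatigue.

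These points reduce the size of the problem but do not remove it. The persistence question sits inside the primary analysis with no condition attached, and with one test per scale at ρ = 0.8 the figure is still 14%. Leaving the tests unspecified widens the later choice of result.

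**Conclusion.** The concern holds in a limited form. The plan applies 0.05 to every test and gives no testing order, key secondary outcome or time, or exploratory label for the clinical scales. The chance of at least one false positive ranges from 11–19% to 24–71%, depending on which tests are meant, and is above 5% on every reading tabulated. These figures assume no true effect anywhere and a common correlation of 0 to 0.8, neither of which comes from the documents. They do not show that a false finding is likely, and they do not affect the error rate of a single 24 h SSI test. This is an inexpensive improvement that should be made; it is not a flaw in the primary comparison.

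**What to change.** Add one paragraph to the Statistics section.

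1. Test the SSI change at 24 h first, at two-sided 0.05.
2. Only if it is significant, continue through a short order stated in advance, each step at two-sided 0.05, stopping at the first non-significant result. One example is MADRS at 24 h, then SSI at 48 h for persistence. The order should not put the 48 h result ahead of 24 h outcomes: the Design section lets patients with less than 50% improvement receive their regular medication in phase 2, which may blur the 48 h contrast.
3. Report all other scales and times, the CADSS subscores and the component items as estimates with 95% confidence intervals, labelled exploratory and without significance claims.
4. Present CADSS and YMRS as descriptive safety summaries by arm.

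This takes SSI change as the sole primary outcome, as in the Design section. The Statistics section also names two dichotomous primary outcomes, and that conflict must be reconciled separately.

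The cost is that a later step cannot be claimed if an earlier one fails. No new data are needed and the 24 h SSI test loses no power. A Bonferroni split would cost more. At 0.05/6 = 0.0083 per test, power for d = 0.7 with an assumed 30 per arm falls from 77% to 53%.
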